6.5.1 Dose escalation guidelines

Dose escalation beyond the dose of 40 mg BID, 80 mg QD or 200 mg BID (for patients harboring the T315I mutation) is not permitted

6.5.2 Dose modifications

For patients who do not tolerate the protocol-specified dosing schedule, dose interruptions and/or reductions are either recommended or mandated in order to allow the patient to continue the study treatment.

These dose modifications are summarized in [Table 6-2](#). The dose reduction indicated as “recommendations” is provided to assist investigators in the event the patient experiences toxicity. However, deviations from “mandatory” dose interruptions and/or reductions are not allowed and mandatory interruptions or reductions must be strictly followed. Re-escalation to asciminib 40 mg BID is permitted if a change in the patient’s individual benefit/risk assessment at the lower dose level is seen. Re-escalation will be allowed only once for any given patient. Permanent treatment discontinuation is mandatory for specific events indicated as such in [Table 6-2](#). Any dose changes must be recorded on the Dosage Administration Record eCRF.

A patient must discontinue treatment with Asciminib if, after treatment is resumed at a lower dose level, the toxicity recurs with the same or worse severity, except for recurrence of cytopenias ([Table 6-2](#)). If a patient requires a dose interruption of > 28 days for each non-hematologic toxicity, then the patient must be discontinued from the study treatment. If a hematologic toxicity (cytopenia Grade 3 or 4) lasts for more than 42 days without recovery to at least a Grade 2, despite TKI interruption and adequate management (including hematopoietic growth factors), then the patient must be discontinued from the study treatment.

These dose changes must be recorded on the appropriate case report form (CRF).

Table 6-2 Criteria for dose reduction / interruption and re-initiation of asciminib treatment for adverse drug reactions.

| Dose modifications for asciminib | |
|---|--|
| Please note that if a patient requires a dose interruption of > 28 days for each toxicity, then the patient must be discontinued from the study treatment | |
| Worst toxicity CTCAE Grade 5 | Asciminib |
| Investigations (Hematologic) If a hematologic toxicity (cytopenia Grade 3 or 4) lasts for more than 42 days without recovery to at least a Grade 2, despite TKI interruption and adequate management (including hematopoietic growth factors), then the patient must be discontinued from the study treatment. | |
| Neutropenia (ANC) | |
| Grade 1 (ANC < LLN – 1.5 x 10 ⁹ /L) | Recommendation: Maintain dose level |
| Grade 2 (ANC < 1.5 – | Recommendation: Maintain dose level |

| Dose modifications for asciminib | |
|---|--|
| Please note that if a patient requires a dose interruption of > 28 days for each toxicity, then the patient must be discontinued from the study treatment | |
| Worst toxicity CTCAE Grade 5 | Asciminib |
| 1.0 x 10 ⁹ /L) | |
| Grade 3 (ANC < 1.0 – 0.5 x 10 ⁹ /L) | Mandatory: Hold dose until resolved to ≤ Grade 2 (recheck CBC 2x/week), then: if resolved in ≤ 14 days, then maintain dose level If resolved in > 14 days, then reduce dose ↓ 1 dose level |
| Grade 4 (ANC < 0.5 x 10 ⁹ /L) | Mandatory: Hold dose until resolved to ≤ Grade 2, (recheck CBC 2x/week), then: if resolved in ≤ 14 days, then maintain dose level if resolved in > 14 days, then reduce dose ↓ 1 dose level |
| Febrile neutropenia (ANC < 1.0 x 10 ⁹ /L, fever ≥ 38.5°C) | Mandatory: Hold dose until resolved, then reduce dose ↓ 1 dose level |
| Thrombocytopenia | |
| Grade 1 (PLT < LLN – 75 X 10 ⁹ /L) | Recommendation: Maintain dose level |
| Grade 2 (PLT < 75 - 50 x 10 ⁹ /L) | Recommendation: Maintain dose level |

| Dose modifications for asciminib | |
|---|---|
| Please note that if a patient requires a dose interruption of > 28 days for each toxicity, then the patient must be discontinued from the study treatment | |
| Worst toxicity CTCAE Grade 5 | Asciminib |
| Grade 3 (PLT < 50 - 25 x 10 ⁹ /L) | Mandatory: Hold dose until resolved to ≤ Grade 2 (recheck CBC 2x/week), then: if resolved in ≤ 14 days, then maintain dose level if resolved in > 14 days, then reduce dose ↓ 1 dose level |
| Grade 4 (PLT < 25 x 10 ⁹ /L) | Mandatory: Hold dose until resolved to ≤ Grade 2 (recheck CBC 2x/week), then: if resolved in ≤ 14 days, then maintain dose level if resolved in > 14 days, then reduce dose ↓ 1 dose level |
| Recurrence of all cytopenias | Recommendation: For recurrent Grade 3-4 cytopenias: If resolved to ≤ Grade 2 in ≤ 14 days, then maintain dose level If resolved in > 14 days, then reduce asciminib and imatinib dose ↓ 1 dose level |
| Non-hematologic adverse reactions except where further specified in individual sections | |
| Grade 1 | Recommendation: Maintain dose level |
| Grade 2 | Recommendation: Hold dose until resolved to ≤ Grade 1, then maintain dose level |
| Grade 3 | Mandatory: Hold dose until resolved to ≤ Grade 1, then reduce dose ↓ 1 dose level |
| Grade 4 | Mandatory: Permanently discontinue patient from study drug treatment. |
| Investigations (Renal) | |

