
Table 6-3 Dose reduction steps for asciminib

| Dose reduction* | | |
|---|--|---|
| | Starting dose level – 0 | Dose level – 1 |
| Asciminib 40 mg BID | 40 mg tablet BID (total daily dose 80 mg) | 20 mg tablet BID (total daily dose 40 mg) |
| Asciminib 80 mg QD | 40 mg tablet + 40 mg tablet = 80 mg once daily | 40 mg tablet once daily |
| Asciminib 200 mg BID | 40 mg tablet x 5 = 200 mg BID | 40 mg tablet x 5 = 200 mg once daily |
| *Dose reduction should be based on the worst toxicity demonstrated at the last dose. | | |
| Asciminib dose reduction below total daily 40 mg is not allowed. 20 mg tablets will be dispensed to patients in the instance of dose reduction. | | |

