6.7 Preparation and dispensation

The investigator or responsible site personnel must instruct the patient or caregiver to take the study drugs as per protocol. Study drug(s) will be dispensed to the patient by authorized site personnel only. All dosages prescribed to the patient and all dose changes during the study must be recorded on the Dosage Administration Record eCRF.

Each study site will be supplied with study drug in packaging as described under investigational drugs section.

A unique medication number is printed on the study medication label.

The IRT will select the study treatment to dispense to the subject. The study medication has a 2-part label (base plus tear-off label), immediately before dispensing the package to the subject, site personnel will detach the outer part of the label from the package and affix it to the subject's source document.

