## **Dose changes, interruptions or permanent discontinuations**

The number of patients, who have dose reductions, dose interruptions or permanent discontinuations, and the reasons, will be summarized separately for all the three study cohorts.

‘Dose Reduced’, ‘Dose Interrupted’ and ‘Dose Permanently Discontinued’ fields from the DAR eCRF pages will be used to determine the dose reductions, dose interruptions, and permanent discontinuations, respectively.

The corresponding fields, ‘Reason for Dose Reduction’, ‘Reason for Dose Interruption and ‘Reason for Permanent Discontinuation’ will be used to summarize the reasons.

A dose change occurs when total daily dose is different from the most recently planned dose. For patients in Cohort A, there is only one planned dose, i.e., 40 mg b.i.d. For patients in Cohort B, there is only one planned dose, i.e., 80 mg/day QD. For patients in Cohort C, the initial planned dose is 200 mg b.i.d i.e., 400 mg/day.

For summarizing interruptions and reasons, multiple entries for interruption that are entered on consecutive days with different reasons will be counted as separate interruptions. However, if the reason is the same in the mentioned multiple entries on consecutive days, then it will be counted as one interruption.

**Reduction:** A dose reduction is where the actual total daily dose is lower than the most recently planned dose. Therefore, any dose reduction to correct a dosing error will not be considered a dose reduction. Only dose reduction is collected in the eCRF and will be summarized for the patient’s data available.

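### Section 6.5.2 names 40 mg BID as the only re-escalation dose for all patients, which fits Cohort A but not Cohorts B and C

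*Protocol*

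**What the plan says.** Protocol Section 6.5.2 covers any patient who cannot tolerate the assigned dosing, and Section 8.1.3 sends patients on all three regimens to Section 6.5 for dose modification. On going back up, Section 6.5.2 says "Re-escalation to asciminib 40 mg BID is permitted if a change in the" patient's benefit and risk at the lower level is seen, and adds: "Re-escalation will be allowed only once for any given patient". Neither sentence names a cohort.

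Table 6-3 gives each cohort its own starting dose and one reduced level:

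- Cohort A starts at 40 mg BID and reduces to 20 mg BID.
- Cohort B starts at "40 mg tablet + 40 mg tablet = 80 mg once daily" and reduces to one 40 mg tablet once daily.
- Cohort C starts at 200 mg BID and reduces to "40 mg tablet x 5 = 200 mg once daily".

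Section 6.5.1 says that "Dose escalation beyond the dose of 40 mg BID, 80 mg QD or 200 mg BID" (the last for T315I patients) is not allowed. Section 6.1.1 says that dosing follows the assigned cohort. Section 6.7 says that the IRT selects what is dispensed. None of these three sections says what dose a reduced patient in Cohort B or C may return to.

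**The concern.** The sentence is operative dosing text that applies to three cohorts but names a dose that belongs to one. A site with a reduced Cohort B or C patient must either work out the right target itself or follow the words on the page.

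For Cohort B, what would be at stake is the schedule. Cohorts A and B take the same daily total and differ only in once-daily against twice-daily dosing, and Section 4.1 gives the once-daily schedule as one of the questions behind the study. For Cohort C, Section 6.3.2 describes 200 mg BID as the dose this population requires. A reduced patient whose benefit/risk balance has changed has no stated way back to it.

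**Working it through.** The check compares the named target with each cohort's doses in Table 6-3.

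**Formula.** Daily total = mg per administration × administrations per day.

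**The plan's own totals.** Table 6-3 states 80 and 40 mg/day for Cohort A: 40 × 2 = 80 and 20 × 2 = 40, which agree. SAP Section 2.4.1 states 400 mg/day for Cohort C: 200 × 2 = 400, which agrees.

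**Named target.** 40 mg BID = 40 × 2 = 80 mg/day.

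| Cohort | Starting dose | Reduced dose | Target minus reduced dose | Target as share of starting total | Starting schedule restored? |
|---|---|---|---|---|---|
| A | 40 × 2 = 80 mg/day | 20 × 2 = 40 mg/day | 80 − 40 = +40 mg/day (+100%) | 80/80 = 100% | Yes |
| B | 80 × 1 = 80 mg/day | 40 × 1 = 40 mg/day | 80 − 40 = +40 mg/day (+100%) | 80/80 = 100% | No: BID instead of QD |
| C | 200 × 2 = 400 mg/day | 200 × 1 = 200 mg/day | 80 − 200 = −120 mg/day (−60%) | 80/400 = 20% | Not applicable: the target is a further reduction |

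So the rule restores dose and schedule in Cohort A, and the daily total but not the schedule in Cohort B. In Cohort C it cannot be used.

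**Does another section supply the missing targets?** Section 6.5.1 sets an upper limit, and an upper limit is not permission to go back up. The opening line of Section 6.5 says that dose adjustments are not permitted, and Section 6.5.2 then sets out what is allowed. A return to the starting dose therefore needs its own permission. Only 40 mg BID has one.

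**With each patient returned to their own starting dose.** Cohort A goes from 40 to 80 mg/day, B from 40 to 80 mg/day on its QD schedule, and C from 200 to 400 mg/day. All three stay within the Section 6.5.1 ceilings.

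**The case against.** The strongest reply is that re-escalation means going back to a dose the patient has already had. A Cohort B patient was never on 40 mg BID, and a Cohort C patient on 200 mg/day cannot escalate to 80 mg/day. On that reading the sentence speaks only to Cohort A. It also permits and does not require. Section 6.1.1 ties dosing to the assigned cohort, and the IRT selects the supply. This stands in part: a careful site would probably not make the switch, and a correctly configured IRT should discourage it.

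It does not close the gap, because the text then says nothing for B and C, and two ordinary readings of that silence disagree. From the opening of Section 6.5, what is not listed is not allowed, so B and C may not re-escalate. From the ceilings in Section 6.5.1, each cohort may return to its own starting dose. Barring re-escalation in Cohort C could be deliberate, since Section 4.2 reports a trend to more discontinuations for adverse events, dose-limiting toxicities and grade 3/4 events as dose rises. The protocol does not say so.

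A reader might also infer a conflict with the SAP, which states "For patients in Cohort B, there is only one planned dose, i.e., 80 mg/day QD". The documents do not support that. SAP Section 2.4.1 says the same of Cohort A, whose patients may nevertheless reduce to 20 mg BID. The planned dose there is the reference for classifying dose changes. It does not limit which doses are permitted.

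**Conclusion.** The point holds and is minor. The only re-escalation dose named in Section 6.5.2 is correct for Cohort A. Taken literally, it permits the other arm's schedule in Cohort B, and it is unusable in Cohort C. No hypothesis is tested and the study is not powered to compare cohorts, so no test, sample size or error rate changes. The documents do not project how many patients will reduce or re-escalate, so the number affected is unknown. The conclusion rests on Table 6-3 and on the absence of any other re-escalation permission in either document.

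Two inferences about the data go too far. The SAP says "A dose change occurs when total daily dose is different from the most recently planned dose". A Cohort B patient on 40 mg BID takes 80 mg/day against 80 planned, so this definition would not count a change. A reader might conclude that the switch would be lost, or that the patient listings would reveal it. Neither is established. Section 6.6.1 says that the dosing record collects the total daily dose with dates. Section 6.7 says "All dosages prescribed to the patient and all dose changes during the study must be recorded on the Dosage Administration Record eCRF", and the glossary's examples of a dosage include frequency. The eCRF layout is not in the documents, so whether the schedule is recorded is unknown.

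**What to change.** Replace the re-escalation sentence in Section 6.5.2 with wording such as: *Re-escalation to the starting dose of the patient's own cohort in Table 6-3 (Cohort A: 40 mg BID; Cohort B: 80 mg QD; Cohort C: 200 mg BID) is permitted once if the balance of benefit and risk at the reduced dose has changed for that patient.* If re-escalation is not intended in Cohort B and/or C, state that instead. Check that the IRT holds the same target for each cohort.

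Under Section 14.1 this needs a written amendment with IRB/IEC approval, and health authority approval where required. It can go into the next amendment and needs no new visits or patients.

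No SAP change is proposed for now. Counting a QD/BID switch at an unchanged daily total as a dose change would need schedule data, and SAP Section 2.4.1 says that dose reduction is the only such change the eCRF collects. If the sponsor confirms that the schedule is captured, one line in that section would be enough.

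The documents do not say whether dosing is complete. If it is, the sponsor should check whether any re-escalated Cohort B patient received 40 mg BID, using IRT or source records if the dosing record holds only daily totals, and state the answer in the clinical study report.

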| > 3.0 - 5.0 x ULN if baseline was normal; 3.0 - 5.0 x baseline if baseline was abnormal | Recommendation: Maintain dose level. Repeat LFTs ^b as soon as possible, preferably within 48-72 hours from awareness of the abnormal results; if abnormal lab values are confirmed upon the repeat test, then monitor LFTs ^b weekly, or more frequently if clinically indicated, until resolved to ≤ 3.0 x ULN if baseline was normal or 1.5 - 3.0 x baseline if baseline was abnormal |

| Dose modifications for asciminib | |
|---|--|
| Please note that if a patient requires a dose interruption of > 28 days for each toxicity, then the patient must be discontinued from the study treatment | |
| Worst toxicity CTCAE Grade 5 | Asciminib |
| > 5.0 - 10.0 x ULN if baseline was normal; 5.0 - 10.0 x baseline if baseline was abnormal | Mandatory: Hold dose. Repeat LFTs ^b as soon as possible, preferably within 48-72 hours from awareness of the abnormal results; monitor LFTs ^b weekly, or more frequently if clinically indicated, until resolved to ≤ 3.0 x ULN if baseline was normal or 1.5 - 3.0 x baseline if baseline was abnormal: Then If resolved in ≤ 14 days, maintain dose level If resolved in > 14 days, reduce dose ↓ 1 dose level |
| > 10.0 - 20.0 x ULN if baseline was normal; > 10.0 - 20.0 x baseline if baseline was abnormal | Mandatory: Hold dose. Repeat LFTs ^b as soon as possible, preferably within 48-72 hours from awareness of the abnormal results; monitor LFTs ^b weekly, or more frequently if clinically indicated, until resolved to ≤ 3.0 x ULN if baseline was normal or 1.5 - 3.0 x baseline if baseline was abnormal. Then reduce dose ↓ 1 dose level. |
| > 20.0 x ULN if baseline was normal; >20.0 x baseline if baseline was abnormal | Mandatory: Hold dose. Repeat LFTs ^b as soon as possible, preferably within 48-72 hours from awareness of the abnormal results; monitor LFTs ^b weekly, or more frequently if clinically indicated, until resolved to ≤ 3 x ULN (or ≤ 5 x ULN for patients with baseline value > 3.0 -5.0 x ULN), then resume treatment at reduce dose ↓ 1 dose level. Only 1 dose reduction is allowed; if reoccurs at > 5 x ULN, discontinue patient from study drug treatment. |

| Dose modifications for asciminib | |
|---|---|
| Please note that if a patient requires a dose interruption of > 28 days for each toxicity, then the patient must be discontinued from the study treatment | |
| Worst toxicity CTCAE Grade 5 | Asciminib |
| Combined ^c elevations of AST or ALT and total bilirubin | |
| 
For patients with normal baseline ALT and AST and total bilirubin value:
 
AST or ALT >3.0 x ULN combined with total bilirubin >2.0 x ULN without evidence of cholestasis^d
 
For patients with elevated baseline AST or ALT or total bilirubin value [AST or ALT >2 x baseline AND > 3.0 x ULN]
 | 
Mandatory: Permanently discontinue patient from study drug treatment. Repeat as soon as possible, preferably within 48 hours from awareness of the abnormal results, then with weekly monitoring of LFTs^b), or more frequently if clinically indicated, until AST, ALT, or bilirubin have resolved to baseline or stabilization over 4 weeks. Refer to Section 6.5.3 for additional follow-up evaluations as applicable.
 |
| Investigation (metabolic) | |
| Asymptomatic amylase and/or lipase elevation | |
| Grade 1 (> ULN - 1.5 x ULN) | Recommendation: Maintain dose level, measure 2x week |
| Grade 2 (> 1.5 - 5.0 x ULN) | Recommendation: Maintain dose level, measure 2x week |
| Grade 3 (> 5.0 x ULN) | Mandatory: Hold dose until resolved to ≤1.5 x ULN or baseline, then: If resolved in ≤ 7 days, then reduce dose ↓ 1 dose level If resolved in > 7 days, then discontinue treatment and obtain appropriate imaging (i.e., MRI, CT scan or ultrasound). |
| Grade 4 (> 5.0 x ULN and with signs and symptoms) | Mandatory: Permanently discontinue patient from study drug treatment. Obtain appropriate imaging (i.e., MRI, CT scan or ultrasound). |

| Dose modifications for asciminib | |
|---|---|
| Please note that if a patient requires a dose interruption of > 28 days for each toxicity, then the patient must be discontinued from the study treatment | |
| Worst toxicity CTCAE Grade 5 | Asciminib |
| Vascular disorders | |
| Hypertension | |
| Systolic BP 140-159 mm Hg or Diastolic BP 90-99 mm Hg | Recommendation: maintain dose level. Initiate antihypertensive drug/increase the dose of current antihypertensive drug or change treatment plan as per investigator assessment |
| Systolic BP ≥160 mm Hg or Diastolic BP ≥100 mm Hg | Mandatory: Hold dose until resolved ≤ Grade 1/baseline, then reduce dose ↓ 1 dose level. Initiate antihypertensive drug/increase the dose of current antihypertensive drug or change treatment plan as per investigator assessment |
| CTCAE Grade 4 | Mandatory: Permanently discontinue patient from study drug treatment. |
| Gastro intestinal | |
| Pancreatitis | |
| Grade 2 (radiologic findings for pancreatitis as per CTCAE v5, for increased enzymes please see table for asymptomatic amylase and/or lipase elevation) | Mandatory: If asymptomatic radiologic pancreatitis, hold treatment until recovery of the radiologic findings. If treatment delay is ≤ 21 days, then reduce dose ↓ 1 dose level. If treatment delay > 21 days, discontinue treatment and keep monitoring with appropriate imaging (i.e., MRI, CT scan or ultrasound). |
| Grade ≥ 3 | Mandatory: Permanently discontinue patient from study drug treatment. Obtain appropriate imaging (i.e., MRI, CT scan or ultrasound). |
| Diarrhea*** | |
| Grade 1 | Recommendation: Maintain dose level but, initiate anti-diarrhea treatment |
| Grade 2 | Recommendation: Hold dose until resolved to ≤ grade 1, then maintain dose level. If diarrhea returns as ≥ grade 2, then hold dose until resolved to ≤ grade 1, then reduce dose ↓ 1 dose level |
| Grade 3 | Recommendation: Hold dose and discontinue patient from study drug treatment |
| Grade 4 | Mandatory: Permanently discontinue patient from study drug treatment |

| Dose modifications for asciminib | |
|--|--|
| Please note that if a patient requires a dose interruption of > 28 days for each toxicity, then the patient must be discontinued from the study treatment | |
| Worst toxicity CTCAE Grade 5 | Asciminib |
| Skin and subcutaneous tissue disorders | |
| Rash/photosensitivity | |
| Grade 1 | Recommendation: Maintain dose level. Consider to initiate appropriate skin toxicity therapy (such as antihistamines, topical corticosteroids and low-dose systemic corticosteroids) |
| Grade 2 | Recommendation: Maintain dose level, but initiate/intensify appropriate skin toxicity therapy (such as antihistamines, topical corticosteroids and low-dose systemic corticosteroids) |
| Grade 3, despite skin toxicity therapy | Recommendation: Hold dose until resolved to Grade ≤ 1, then: If resolved in ≤ 7 days, then reduce dose ↓ 1 dose level If resolved in > 7 days (despite appropriate skin toxicity therapy), then discontinue patient from study drug treatment |
| Grade 4, despite skin toxicity therapy | Mandatory: Permanently discontinue patient from study drug treatment. |
| General disorders and administration site conditions | |
| Fatigue/ Asthenia | |
| Grade 1 or 2 | Recommendation: Maintain dose level |
| Grade 3 | Recommendation: Hold dose until resolved to ≤ grade 1, then : If resolved in ≤ 7 days, then maintain dose level If resolved in > 7 days, then reduce dose ↓ 1 dose level |
| 
All dose modifications should be based on the worst preceding toxicity.
 
^a Common Toxicity Criteria for Adverse Events (CTCAE Version 5)
 
^b Core LFTs consist of ALT, AST, total bilirubin (fractionated [direct and indirect], if total bilirubin > 2.0 x ULN), and alkaline phosphatase (fractionated [quantification of isoforms], if alkaline phosphatase > 2.0 x ULN).
 
^c “Combined” defined as total bilirubin increase to the defined threshold concurrently with ALT/AST increase to the defined threshold
 
If combined elevations of AST or ALT and total bilirubin do not meet the defined thresholds, please follow the instructions for isolated elevation of total bilirubin and isolated elevation of AST/ALT, and take a conservative action based on the degree of the elevations (e.g. discontinue treatment at the situation when hold dose is needed for one parameter and discontinue treatment is required for another parameter). After all elevations resolve to the defined thresholds that allow treatment re-initiation, re-start the treatment either at the same dose or at one dose lower if meeting a criterion for dose reduction
 
^d “Cholestasis” defined as ALP elevation (>2.0 x ULN and R value <2) in patients without bone metastasis, or elevation of ALP liver fraction in patients with bone metastasis
 
Note: The R value is calculated by dividing the ALT by the ALP, using multiples of the ULN for both values. It denotes whether the relative pattern of ALT and/or ALP elevation is due to cholestatic (R ≤ 2), hepatocellular (R ≥ 5), or mixed (R >2 and < 5) liver injury
 
* Note: If total bilirubin > 3.0 x ULN is due to the indirect (non-conjugated) component only, and hemolysis as the etiology has been ruled out as per institutional guidelines (e.g., review of peripheral blood smear and haptoglobin determination), then ↓ 1 dose level and continue treatment at the discretion of the investigator.
 
** Note: A CT scan or other imaging study to assess the pancreas, liver, and gallbladder must be performed within 1 week of the first occurrence of any ≥ Grade 3 of amylase and/or lipase. If asymptomatic Grade 2 elevations of lipase and/or amylase occur again at the reduced dose, patients will be discontinued permanently from study treatment.
 
*** Note: antidiarrheal medication is recommended at the first sign of abdominal cramping, loose stools or overt diarrhea
 | |

Table 6-3 Dose reduction steps for asciminib

| Dose reduction* | | |
|---|--|---|
| | Starting dose level – 0 | Dose level – 1 |
| Asciminib 40 mg BID | 40 mg tablet BID (total daily dose 80 mg) | 20 mg tablet BID (total daily dose 40 mg) |
| Asciminib 80 mg QD | 40 mg tablet + 40 mg tablet = 80 mg once daily | 40 mg tablet once daily |
| Asciminib 200 mg BID | 40 mg tablet x 5 = 200 mg BID | 40 mg tablet x 5 = 200 mg once daily |
| *Dose reduction should be based on the worst toxicity demonstrated at the last dose. | | |
| Asciminib dose reduction below total daily 40 mg is not allowed. 20 mg tablets will be dispensed to patients in the instance of dose reduction. | | |

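### After a first asymptomatic Grade 3 amylase/lipase elevation that resolves within 7 days, Table 6-2 permits restart before the scan it already requires

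*Protocol*

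**What the plan says.** Four parts of Protocol Section 6.5.2 bear on this.

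- **Table 6-2, asymptomatic amylase/lipase elevation, Grade 3 (above 5 x ULN).** The action is mandatory: "Hold dose until resolved to ≤1.5 x ULN or baseline, then: If resolved in ≤ 7 days, then reduce dose" by one level. The slower branch reads "If resolved in > 7 days, then discontinue treatment and obtain appropriate imaging (i.e., MRI, CT scan or ultrasound"). Within this row, imaging appears only in the slower branch, together with discontinuation.
- **Table 6-2, double-asterisk note.** It states: "A CT scan or other imaging study to assess the pancreas, liver, and gallbladder must be performed within 1 week of the first occurrence". The trigger is an amylase or lipase value of Grade 3 or higher. The scan is therefore compulsory for fast resolvers too, with a deadline counted from the first occurrence.
- **Table 6-2, Pancreatitis, Grade 2.** Also mandatory: "If asymptomatic radiologic pancreatitis, hold treatment until recovery of the radiologic findings". Then, "If treatment delay is ≤ 21 days, then reduce dose" by one level; a longer delay means discontinuation.
- **Safeguards after restart.** Treatment must stop "if, after treatment is resumed at a lower dose level, the toxicity recurs with the same or worse severity" (cytopenias excepted). The double-asterisk note adds: "If asymptomatic Grade 2 elevations of lipase and/or amylase occur again at the reduced dose, patients will be discontinued permanently from study treatment".

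**The concern.** The Pancreatitis row shows that the sponsor does not regard enzyme recovery as enough once imaging is positive: the hold then lasts until the radiologic findings recover. Yet the 7-day branch of the enzyme row releases the hold on the enzyme value alone, while the compulsory scan may still be outstanding. What is at stake is a short period of dosing, at the reduced level, in a patient whom the protocol's own rules would have kept off drug had the scan come first.

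The pancreas is a recognised target organ for this drug. Section 1.1.2.1 lists it among the toxicology findings. Section 1.1.2.2 names increased lipase as the most common Grade 3/4 event, at 17.1% (grades combined, so not a rate for this branch). Section 4.2 reports pancreatitis in the phase I study.

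**Working it through.** The plan states no figure to reproduce. The check is whether any text orders the two steps and, if none does, how long the gap can be.

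**Is restart tied to the scan?**

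| Place | Starts or releases | Clock | Mentions the other step? |
|---|---|---|---|
| Grade 3 enzyme row, 7-day branch | restart one level lower | enzyme at or below 1.5 x ULN or baseline | no scan condition |
| Double-asterisk note | scan | 1 week from first occurrence | no restart condition |
| Pancreatitis Grade 2 row | hold | once a finding is known | acts only after the scan |
| Sections 6.5.2 (text) and 6.5.3 | general rules, follow-up | n/a | no imaging condition |

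If r is the restart day and s the scan day, both rules are met by any r < s ≤ 7. For example, restart on day 3 and scan on day 7 is fully compliant. In the text available, the double-asterisk marker is not attached to the enzyme row, possibly because of extraction, but the note names both enzymes, so its scope is clear. Section 4.4 points to a Section 6.5.4 for toxicity management; neither the contents list nor the text supplied contains one, so no restart condition can be read from it.

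**How long can the gap be?**

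Day 0 is the sample with the first Grade 3 value, and the scan is due by day 7.

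- t1 = days to the first result and hold
- r1 = days from hold to recheck
- t2 = days to the recheck result
- Restart day = t1 + r1 + t2
- Gap = 7 − restart day, not below 0, if the scan is left to the deadline

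The Grade 3 row gives no recheck interval. I assume 3 to 4 days, from the twice-weekly measurement in the Grade 1 and 2 rows. Section 8.3.1 makes chemistry central by default and restricts local testing, but gives no turnaround time; I show 0, 1 and 2 days.

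| t1 = t2 | r1 | Restart day | Gap (days) |
|---|---|---|---|
| 0 | 1 | 0+1+0 = 1 | 7−1 = 6 (theoretical maximum) |
| 0 | 3 to 4 | 3 to 4 | 4 to 3 |
| 1 | 3 to 4 | 1+3+1 = 5 to 1+4+1 = 6 | 2 to 1 |
| 2 | 3 to 4 | 2+3+2 = 7 to 2+4+2 = 8 | 0 |

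Any scan before day 7 shortens or removes the gap. If the enzyme takes longer than 7 days to resolve, treatment is discontinued and the question does not arise.

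**How many patients?** This cannot be estimated. The documents give no rate for Grade 3 alone, no share resolving within 7 days, no scan timing and no scan positivity.

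**The case against.** The strongest reply is that the table permits this order without requiring it. The enzyme row sets no deadline for restart, and Section 6.5.2 allows a non-hematologic interruption of up to 28 days, so an investigator can wait for the scan without any deviation. The row and the note do not contradict each other. The row covers asymptomatic patients only, the enzyme must first have recovered, dosing resumes at a lower level, a positive scan triggers the hold, and recurrence ends treatment. No document shows that radiologic pancreatitis occurs in asymptomatic patients whose enzymes recover within a week. All of this stands. It limits the size of the point but leaves the order of the two steps unstated.

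A reader might also infer a stronger harm: that early restart uses up the only listed dose reduction. The patient is then at level −1, the Pancreatitis row asks for a further reduction, Table 6-3 lists no lower level, and "Asciminib dose reduction below total daily 40 mg is not allowed" (which binds in Cohorts A and B). The documents do not support blaming this on scan timing. In either order the same patient meets the same two rows, each asking for one level. If reductions add up across rows, the scan-first patient also needs two and also has no lower level. If one episode earns one reduction, the restart-first patient has already taken it and can resume at level −1. The closing notes to Table 6-2 base modifications on the worst preceding toxicity, which favours one reduction per episode; the footnote to Table 6-3, which refers to the last dose, can be argued either way. The absence of a level −2 is a general feature of Table 6-3.

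**Conclusion.** The gap in the text is real, and confidence in that reading is high. After a first asymptomatic Grade 3 amylase or lipase elevation that resolves within 7 days, a compliant site may restart before the compulsory scan and so re-dose a patient whom the Pancreatitis row would have kept on hold.

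The point is minor. The exposure is at most 6 days in theory and about 0 to 4 days under the assumed recheck interval and turnaround, always at the reduced dose. It should not be read as a contradiction within the table, as an instruction to restart early, or as a threat to any endpoint or analysis. The clinical consequence is unquantified because the documents give no basis for a count.

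**What to change.** Two wording changes in Table 6-2, for all cohorts:

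1. To the imaging sentence of the double-asterisk note, add: *and before any restart of study treatment*.
2. In the 7-day branch of the Grade 3 enzyme row, state: *if resolved in ≤ 7 days and imaging shows no pancreatitis, reduce dose 1 dose level; if imaging shows pancreatitis, follow the Pancreatitis row (one dose reduction in total for the episode)*.

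The 7-day test should continue to refer to enzyme resolution only, so that waiting for a scan moves nobody into the discontinuation branch. The branch for slower resolution is unchanged. The bracketed words also settle how the two reduction rows combine.

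The cost is one table row and one footnote. The 7-day branch gains no procedure, because the note already requires the scan. The downside is that restart may wait a few days for it, in a patient already on hold. Section 6.5.2.1 already uses this device for QTcF prolongation, where electrolyte abnormalities must be corrected before treatment resumes.
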